5.1 Analysis of primary outcome

The BALANCE Trial will be conducted, analyzed and reported according to CONSORT guidelines, including analyzing patients in the groups to which they were assigned (adherent to the intention-to-treat principle).¹⁴ We will also include a per-protocol analysis. Inferences that 7 day treatment is non-inferior to 14 day treatment will be stronger if this finding is confirmed in both intention-to-treat and per protocol analyses.¹⁵ We will also perform a modified intention-to-treat analysis (mITT), excluding patients that die before day 7 of treatment, given that these patients die prior to divergence in treatment assignment.¹⁶ The primary analysis will examine whether 90-day mortality is non-inferior in the 7 vs. 14 day treatment group, as determined by whether the 95.7% confidence interval excludes a 4% absolute increase in mortality. Results will also be reported as relative risks with confidence intervals.

In a secondary adjusted analysis we will use generalized linear mixed models with random effects for center (which was a stratification variable) - with log-link and binomial distribution and report relative risks and confidence intervals. If this model fails to converge we will use modified Poisson regression.¹⁷

5.2 Analysis of secondary outcomes

Mortality rates at other time points will be calculated in a similar manner to 90-day mortality. We hypothesize that mortality rates will be non-inferior with 7 days of treatment using the same 4% non-inferiority margin, and relapse of bacteremia using a 2% absolute margin. Continuous secondary outcomes, including ICU, hospital, ventilation and vasopressor free-days by day 28 will be summarized as means and difference in means with 95% CIs as well as medians and difference in medians using quantile regression. For ICU, hospital, ventilation and vasopressor free-days by 28, a 2-day margin will be used for assessing non-inferiority.

We hypothesize that 7 days of treatment will be superior to 14 days of treatment for: antibiotic allergy and adverse events, rates of *C. difficile* infection in hospital, rates of secondary nosocomial infection/colonization with antimicrobial resistant organisms in hospital, and antibiotic-free days (of 28). The evaluation of allergy and adverse events will be important but these analyses are likely to be underpowered due to low event rates, despite the large trial sample size. Antibiotic allergy and adverse events, *C. difficile* infection and secondary nosocomial infection/colonization with antimicrobial resistant organisms are binary outcomes, and we will examine via chi-square tests of proportions. Antibiotic-free days (of 28) will be summarized as means and difference in means with 95% CIs as well as medians and difference in medians using quantile regression.

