3.2. Definitions for Secondary Outcomes

3.2.1 Hospital all-cause mortality: recorded as alive or dead at hospital discharge following index positive blood culture.

3.2.2 ICU all-cause mortality: recorded as alive or dead at index ICU discharge following index positive blood culture, among all patients diagnosed with bacteremia during ICU admission.

3.2.3 Relapse rate of bacteremia: defined as the recurrence of bacteremia due to original infecting organism (same Genus and species) within 30 days after completing course of adequate antimicrobial therapy.

3.2.4 Intensive care unit length of stay and ICU free days (of 28): ICU length of stay will be defined as the duration between ICU admission (and after the index blood culture) and discharge from the ICU for a consecutive 48-hour period. Durations will be calculated for all patients then separately for patients who died within ICU and those who did not die. ICU-free days (of 28) will be calculated as the cumulative days alive and not in ICU in the first 28 days from collection of the index blood culture; all patients who die within 28 days will be assigned 0 ICU-free days.

3.2.5 Hospital length of stay and hospital-free days of (28) – hospital length of stay will be defined as the duration between index blood culture in hospital and discharge date from hospital. Hospital-free days (of 28) will be calculated as the cumulative days alive and not in hospital in the first 28 days from collection of the index blood culture; all patients who die within 28 days will be assigned 0 hospital-free days.

3.2.6 Duration of mechanical ventilation and ventilator-free days of (28) – duration of mechanical ventilation will be defined as the number of consecutive days receiving invasive (via an endotracheal tube or tracheostomy) for any duration. Non-invasive ventilation, continuous positive airway pressure and high-flow oxygen therapy will not be considered in this analysis. Ventilator-free days (of 28) will be calculated as the cumulative days alive and not receiving invasive mechanical ventilation in the first 28 days from collection of the index blood culture; all patients who die within 28 days will be assigned 0 ventilator-free days.

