The primary analysis will assess whether 7 days of treatment is associated with a non-inferior 90-day mortality rate in comparison to 14 days of treatment. We require 1,686 patients per arm to establish a non-inferiority margin of +4% absolute increase in mortality (baseline mortality 22%)⁵ power 80%, alpha 0.025, one-sided equivalence test). We have inflated this to account for a maximum of 5% loss-to-follow-up, and have incorporated early stopping rules to account for the 3 interim analyses (coefficient 1.024)^{6,7} for a total sample size of 3626. Recent landmark trials in with similar baseline mortality rates have used +4% as a non-inferiority margin;^{8,9} the U.S. FDA has recommended a similar margin for analogous industry-sponsored trials.¹⁰ The PneumA study of 8 vs 15 day treatment for VAP used a non-inferiority margin of 10%,¹¹ as have other recent prominent infectious diseases non-inferiority trials,^{12,13} but we believe lower non-inferiority margins are desirable, when feasible, for the outcome of mortality.

5. Statistical analysis

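### The 2-day margin on mean free days is looser on mortality than the trial's 4-point margin, and a free-day non-inferiority claim does not depend on the mortality result

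*SAP*

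**What the plan says.** Section 5.2 of the SAP sets one margin for four secondary outcomes: "For ICU, hospital, ventilation and vasopressor free-days by 28, a 2-day margin will be used for assessing non-inferiority". These outcomes are to be summarised both as a difference in means with a 95% confidence interval and as a difference in medians from quantile regression. The section does not say which of the two carries the margin.

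Section 3.2 builds death into each score. For hospital-free days, "all patients who die within 28 days will be assigned 0 hospital-free days". The same rule is written for ICU-, ventilator- and vasopressor-free days.

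For mortality, section 5.1 judges the 90-day primary outcome "as determined by whether the 95.7% confidence interval excludes a 4% absolute increase in mortality". Section 5.2 uses the same 4% margin for mortality at other time points. Section 4 argues for the 4% figure and says that smaller margins are preferable for mortality where feasible. The SAP gives no reason for 2 days and does not relate it to the 4% margin. It also does not make a free-day conclusion depend on the mortality result.

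**The concern.** A free-day score treats death as its worst value, so its margin tolerates some excess mortality whether or not that was intended. If the tolerated excess is larger than the one the primary analysis must exclude, the 7-day arm could reach the primary's unacceptable limit and still be called non-inferior on up to four secondary outcomes. As section 5.2 stands, those claims could be reported as support for 7 days even if the mortality margin had not been met.

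**Working it through.** **Inputs from the SAP**
- Section 4: "We require 1,686 patients per arm to establish a non-inferiority margin of +4% absolute increase in mortality"; control mortality 22%; "power 80%, alpha 0.025, one-sided equivalence test".
- Section 4: "We have inflated this to account for a maximum of 5% loss-to-follow-up"; interim-analysis coefficient 1.024; "for a total sample size of 3626".
- Section 5.1: 95.7% two-sided interval for the primary outcome.
- Section 5.2: 2-day free-day margin, 95% interval.
- Section 3.2: death by day 28 scores 0; the maximum is 28.

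**Step 1. The plan's own figures.** With 22% in both arms, a 0.04 margin, one-sided alpha 0.025 and 80% power:

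n = (1.960 + 0.842)² x 2 x 0.22 x 0.78 / 0.04² = 1,684 per arm, against 1,686 stated.

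Total: 2 x 1,686 x 1.024 x 1.05 = 3,625.6, which rounds up to 3,626. The planned size reproduces. Analysable patients after 5% loss: 3,626 x 0.95 / 2 = 1,722 per arm.

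**Step 2. What 4 points can cost.** If survivors average f free days and their durations do not change, an excess mortality d lowers the mean by d x f, and f cannot exceed 28.
- Largest cost of 4 points: 0.04 x 28 = 1.12 days, which is 56% of the margin.
- Smallest mortality excess worth 2 days: 2/28 = 7.1 points.
- At assumed survivor means of 24, 20 and 16 days, 2 days is worth 2/24 = 8.3, 2/20 = 10.0 and 2/16 = 12.5 points.

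Deaths between day 28 and day 90 count in the primary outcome but cost nothing on the score through death, so the actual loss from a 4-point excess at day 90 can only be smaller.

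**Step 3. How often the 2-day rule passes at a true 4-point excess.** Take 22% v 26%, all by day 28, and nothing else different. For survivor mean f and SD s, an arm with mortality p has

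mean = (1 - p) f, variance = (1 - p)(s² + f²) - [(1 - p) f]².

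With SE = sqrt[(v0 + v1)/1,722], where v0 and v1 are the two arm variances,

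P(pass) = Phi[(2 - 0.04 f)/SE - 1.96].

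| Survivor mean (SD), days | Loss | 95% half-width | Expected lower limit | P(pass) |
|---|---|---|---|---|
| 28 (0), extreme case | 1.12 | 0.80 | -1.92 | 0.58 |
| 24 (5), assumed | 0.96 | 0.74 | -1.70 | 0.78 |
| 20 (8), assumed | 0.80 | 0.74 | -1.54 | 0.89 |
| 16 (8), assumed | 0.64 | 0.65 | -1.29 | 0.98 |

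In the extreme case the SDs follow from mortality alone: 28 x sqrt(0.22 x 0.78) = 11.6 and 28 x sqrt(0.26 x 0.74) = 12.3.

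**Step 4. The primary rule at the same excess.** A 95.7% two-sided interval leaves 0.043/2 = 0.0215 in one tail, so a true 4-point excess passes about 2% of the time. In terms of observed data with 22% in the 14-day arm, the 4% rule stops passing at an observed excess of about 1.1 points. In the extreme case the 2-day rule still passes at about 4.3 points.

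**Step 5. Smaller analysis sets.** With an assumed 900 per arm, for example if an outcome were limited to ICU patients, the extreme case has an expected lower limit of -2.22 and passes 35% of the time. The three milder cases pass 51%, 64% and 84% of the time. The 1.12-day ceiling does not depend on sample size; the pass rates do.

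**The case against.** The strongest reply is that the two margins measure different things. One concerns death by day 90. The other concerns a 28-day composite that also carries non-fatal time in ICU, in hospital, on a ventilator or on vasopressors. A margin on such a composite need not equal the mortality margin, and nothing in the SAP says that it must. This stands: the SAP does not contradict itself here. It also means that 1 day cannot be presented as the one correct replacement.

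A second reply is that mortality is already guarded. The primary tests it at 4 points, and section 5.2 applies the same margin to hospital and ICU mortality. This protects the trial's main conclusion. It does not protect the free-day claims, which section 5.2 lets stand alone. Section 3.2.4 does separate ICU length of stay by whether the patient died in ICU, but no such split is written for the free-day scores.

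A third reply is that the arithmetic is for means, and section 5.2 also lists medians. That is correct, and it is why the fix names the summary that carries the margin. No equivalent was computed for medians.

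A reader might go further than the SAP supports in three ways:
- That any excess the primary rules out costs at most 1.12 days. The ceiling belongs to exactly 4 points; 8 points could cost up to 0.08 x 28 = 2.24 days.
- That a 4-point excess is sure to pass. In the case that defines the ceiling it passes only about 58% of the time, and less often in a smaller set.
- That the primary conclusion is compromised. It is not, because the free-day outcomes play no part in the primary rule.

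**Conclusion.** The concern holds as a weakness in four secondary claims. On means, the 2-day margin tolerates at least 7.1 points of excess mortality where the trial's mortality margin is 4. That bound rests only on the 0-to-28 scale, the scoring of death as 0, and unchanged durations among survivors.

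The pass rates of about 58% to 98%, against about 2% for the primary rule, rest on more: 22% v 26% mortality with all deaths by day 28, 1,722 per arm, the margin applied to the difference in means, and no other treatment effect. The survivor means and SDs behind the 78% to 98% are assumptions, since the SAP gives none. The primary analysis and the sample size are unaffected.

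**What to change.** In section 5.2:
1. State that non-inferiority on ICU-, hospital-, ventilator- or vasopressor-free days will be claimed only if 90-day mortality non-inferiority is also shown.
2. Report day-28 mortality and free days among survivors beside each free-day comparison, so that the fatal and non-fatal parts can be seen. The survivor figures are descriptive, because survival is itself an outcome.
3. State that the 2-day margin applies to the difference in means, with the medians as supporting description.

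These changes are SAP wording. They use vital status and durations already collected and need no more patients. The downside is that no free-day non-inferiority claim can be made if the primary fails.

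A tighter margin of about 1 day is optional and for the sponsor to weigh. With 1,722 per arm and no true difference, its power is Phi[1/(SD x sqrt(2/1,722)) - 1.96]: 84% at SD 10, 76% at SD 11 and 69% at SD 12 (SDs assumed). It would not fully close the gap either. One day is worth 1/f in mortality, which is more than 4 points whenever survivors average fewer than 25 free days.

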5.3 Subgroup analyses

The main subgroup analysis will be based on the underlying infectious syndrome causing bacteremia (vascular catheter-related, pneumonia, pyelonephritis, intra-abdominal, skin and soft tissue, other identified source, or

unknown source). We will also perform subgroup analyses based on ICU versus non-ICU enrolments, community- versus hospital-acquisition (>48h post admission), Gram positive versus Gram negative infection, illness severity (APACHE II score of ≥ 25 vs. < 25), vasopressor use on day of randomization and baseline Clinical Frailty Score (≥ 5 vs. < 5).¹⁸ We hypothesize that the non-inferiority of 7 versus 14 days of treatment will be consistent across these subgroups. The subgroup analyses will only be conducted for the primary outcome.

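### Section 5.3 examines APACHE II and the Clinical Frailty Score only as two-level cuts, which loses sensitivity to a graded change in the 7-versus-14-day mortality difference

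*SAP*

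**What the plan says.** SAP section 5.3 makes infectious syndrome the main subgroup factor and lists several others. Two of these are scores, and each is reduced to two groups: "illness severity (APACHE II score of ≥ 25 vs. < 25), vasopressor use on day of randomization and baseline Clinical Frailty Score (≥ 5 vs.", the last of these being compared with frailty scores under 5.

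The purpose is given as a hypothesis: "We hypothesize that the non-inferiority of 7 versus 14 days of treatment will be consistent across these subgroups". The scope is limited to 90-day mortality: "The subgroup analyses will only be conducted for the primary outcome".

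Section 5.3 names no interaction test or model and states no rule for judging consistency. The adjusted model in section 5.1 names only a random effect for center, so neither score enters there on its full scale. The SAP gives no distribution for either score and no expected share of patients above either cut.

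**The concern.** APACHE II takes many values and the Clinical Frailty Score is ordinal. A cut at 25 puts scores of 24 and 25 in opposite groups and treats 25 and 40 as the same. If the 7-versus-14-day difference changes steadily along the score, the two-group comparison uses only part of the evidence for that change.

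The hypothesis in section 5.3 is that the result holds throughout. A reader will want to know whether the mortality difference drifts upward with severity or frailty. A plan that looks at each score through one threshold answers that less well than it could. Section 5.3 states no rationale for 25. The frailty item carries a citation to the source of the scale, which cannot be checked here for support of 5.

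**Working it through.** **Step 1: the plan's own figure.** The SAP states no power or information for the subgroup analyses. Its only related figure is the sample size in section 4: "We require 1,686 patients per arm to establish a non-inferiority margin of +4% absolute increase in mortality (baseline mortality 22"%, with "power 80%, alpha 0.025, one-sided equivalence test".

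- Per arm: (1.960 + 0.842)² × 2 × 0.22 × 0.78 / 0.04² = 7.849 × 0.3432 / 0.0016 ≈ 1,684, against 1,686 stated.
- Total: 2 × 1,686 × 1.024 × 1.05 = 3,625.6, against 3,626 stated.

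The sample size reproduces, and this point does not touch it.

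**Step 2: information kept by a cut, normal score.** Assume a normal score and a treatment effect that changes linearly with it. The information that a two-level version keeps, relative to the linear term, is the squared correlation between the score and its cut: E = φ(z)² / [p(1 − p)], where p is the share above the cut and z the matching normal quantile. The values of p are assumed.

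| Share above cut | φ(z)² | p(1 − p) | Kept | Lost | Equivalent N out of 3,626 |
|---|---|---|---|---|---|
| 50% | 0.1592 | 0.25 | 0.637 | 36% | 2,308 |
| 30% | 0.1209 | 0.21 | 0.576 | 42% | 2,087 |
| 20% | 0.0784 | 0.16 | 0.490 | 51% | 1,776 |

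With only 10% above the cut, the loss would be 66%.

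**Step 3: the same loss as power.** Suppose a two-sided 5% interaction test has 80% power on the full scale. After the cut its power is Φ(√E × (1.960 + 0.842) − 1.960):

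- 50% above: Φ(0.798 × 2.802 − 1.960) = Φ(0.275) ≈ 61%
- 30% above: Φ(0.759 × 2.802 − 1.960) = Φ(0.166) ≈ 57%
- 20% above: Φ(0.700 × 2.802 − 1.960) = Φ(0.001) ≈ 50%

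**Step 4: other shapes.**

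- Skewed (gamma) scores with 10% to 50% above the cut lose 36% to 56%, so the APACHE II range does not depend closely on normality.
- For frailty, nine levels were assumed and cut at 5. Five illustrative distributions lose 17% to 33%. Bell-shaped ones with centers 3 to 5 and spread 1.3 to 2.0 lose about 32% to 57%. The largest loss is at center 3 and spread 1.3, where only about 12% score 5 or more.
- If the effect truly changes in one step at the cut, the two-level analysis loses nothing.

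**Step 5: what the cut does under another reading of consistency.** Suppose instead that each subgroup must exclude +4% with the 95.7% interval used for the primary analysis. Take 20% of 3,626 patients, so about 363 per arm, with 22% mortality in both. The standard error is √(2 × 0.22 × 0.78 / 362.6) = 0.0308, and the half-width is 2.024 × 0.0308 = 6.2 points. The chance of excluding +4% when there is no true difference is Φ(0.04 / 0.0308 − 2.024) ≈ 23%. For half the patients it is about 51%.

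**The case against.** The case for leaving section 5.3 alone is a fair one. Both cuts are prespecified and unambiguous, nothing in the SAP contradicts them, and two-level subgroups are common and easy to report. Severity is also approached through ICU enrolment and vasopressor use. These are secondary analyses. All of this stands, and it keeps the point small. It does not restore the lost sensitivity, because those other factors are two-level as well.

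Three stronger readings are tempting, and the SAP supports none of them.

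- A reader might infer that a fixed 35% to 50% of the information is lost for both scores. The SAP gives no distributions, and for frailty the loss can fall well below or somewhat above that range.
- A reader might infer that the cut makes apparent consistency easy to obtain. That is so only if consistency means a non-significant interaction test, which section 5.3 does not name. If each subgroup must exclude the margin, step 5 shows that small groups make consistency hard to show.
- A reader might infer that harm to the sickest or frailest is the trial's main worry. The SAP does not say so, and it makes infectious syndrome the main subgroup factor.

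The power figures likewise describe an interaction test that the SAP does not specify. They measure the sensitivity of the data as grouped, not the performance of a planned test.

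**Conclusion.** The point holds as a modest improvement. Section 5.3 fixes both scores as two-level factors and plans nothing on the full scale, so sensitivity to a graded change in the mortality difference is given up.

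For APACHE II the loss is about 36% to 51% of the interaction information. This rests on a roughly normal score, linear modification and 20% to 50% of patients above 25, none of which the SAP states. For frailty the loss is about 17% to 57% under assumed nine-level distributions. It is zero for either score if the effect is a true step at the cut. The primary non-inferiority inference and the sample size are not affected.

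**What to change.** Keep the groups at 25 and 5 in section 5.3 for the forest plot. Add, for each score:

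- a treatment-by-score interaction for 90-day mortality with the score on its full scale, entered linearly, on the risk-difference scale so that it matches the absolute margin;
- a restricted cubic spline version as a check on the linear shape;
- a plot of the estimated 7-minus-14-day mortality difference, with its interval, across the score.

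The cost is a few sentences in the SAP and two extra secondary models with their spline checks. No new data should be needed, since assigning patients to the planned groups already requires the scores. The downside is the assumed linear shape, which the spline examines. No planned result is replaced.

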5.4 Frequency of analyses

Three interim analyses occurred for BALANCE, at 1/6 (600 patients), 1/3 (1200 patients) and 2/3 (2400 patients) of total enrollment; we planned to stop at the interim analysis for futility, inferiority or superiority using the O'Brien-Fleming spending function to generate adjusted confidence intervals for the primary endpoint, splitting the type I error at 0.0000007, 0.000452, 0.013, and 0.043 with 99.99%, 99.95%, 98.68% and 95.70% two-sided confidence intervals to give an overall type I error of 2.5%.^{6,7,15} The Data Monitoring Committee (DMC) was guided by a graphical plot indicating mortality differences which would meet futility, inferiority or superiority thresholds. We will perform both frequentist-based and Bayesian-based analyses for the primary outcome at the study's termination. Subgroup analyses were not performed for the interim analyses.

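### With no interim stop for non-inferiority listed, the final 95.7% interval gives the primary claim a one-sided type I error of about 2.15%, not the stated 2.5%, and power of about 79% at the full 5% loss

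*SAP*

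**What the plan says.** - **Interim rule (SAP 5.4).** The looks fall "at 1/6 (600 patients), 1/3 (1200 patients) and 2/3 (2400 patients) of total enrollment". Of them the SAP says "we planned to stop at the interim analysis for futility, inferiority or superiority". The committee's aid was a "graphical plot indicating mortality differences which would meet futility, inferiority or superiority thresholds". Both lists name the same three outcomes, and neither names non-inferiority. The section does not define the futility threshold or say which null hypothesis each interim interval tests.
- **Levels (SAP 5.4).** The boundary is of O'Brien-Fleming type, "splitting the type I error at 0.0000007, 0.000452, 0.013, and 0.043". The matching final interval is among the "95.70% two-sided confidence intervals to give an overall type I error of 2.5"%.
- **Primary decision (SAP 5.1).** Non-inferiority is declared "as determined by whether the 95.7% confidence interval excludes a 4% absolute increase in mortality".
- **Sample size (SAP 4).** The design has 1,686 per arm, 80% power, one-sided alpha 0.025 and a "non-inferiority margin of +4% absolute increase in mortality (baseline mortality 22"%). For the looks, the sponsor states that they "have incorporated early stopping rules to account for the 3 interim analyses (coefficient 1.024"), and the total, with a maximum of 5% loss, is 3626.

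**The concern.** The final test of a hypothesis is made stricter to pay for earlier chances to reject that same hypothesis. Here the primary null is a mortality excess of at least 4 points. A futility or inferiority stop cannot reject it. A superiority stop can, since an interval wholly below 0 is also below +4, but when the true excess is 4 points that is almost impossible. The primary claim thus bears the cost of repeated testing without having been repeatedly tested in any material sense.

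Two stated operating figures are then not those of the design. The 2.5% is not the error rate of the non-inferiority claim. The 1.024 inflation is what a design needs when it can also reject at interim looks; a single test at the reduced level needs more. Anyone reporting the trial would attach the wrong error rate and a slightly optimistic power to its main conclusion.

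**Working it through.** **Inputs.** Margin 0.04, mortality 22%, one-sided alpha 0.025, 80% power, 1,686 per arm, 5% loss, coefficient 1.024 and total 3626 (SAP 4). Looks at information 1/6, 1/3, 2/3 and 1, with two-sided nominal levels 0.0000007, 0.000452, 0.013 and 0.043 (SAP 5.4). Final 95.7% interval against +4% (SAP 5.1).

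**1. The plan's own sample size.** n per arm = (1.960 + 0.8416)² × 2 × 0.22 × 0.78 / 0.04² ≈ 1684, against 1,686 stated. Then 1,686 × 2 × 1.024 × 1.05 = 3625.6, which rounds up to 3626. Both reproduce.

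**2. Final level.** (1 − 0.957)/2 = 0.0215 one-sided, critical value z = 2.0237.

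**3. Alpha spent at the looks under the listed rules.** With true mortality 22% and 26%, the standard errors at 600, 1200 and 2400 patients are 0.03483, 0.02463 and 0.01742. The critical values from the nominal levels are 4.961, 3.508 and 2.484. The probability of a superiority stop is Φ(−z − 0.04/SE):

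| Look | Probability |
|---|---|
| 1/6 | 5.0e-10 |
| 1/3 | 1.4e-7 |
| 2/3 | 8.7e-7 |
| Sum | about 1.0e-6 |

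Inferiority and futility stops can only remove non-inferiority claims.

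**4. Type I error of the primary claim.** From steps 2 and 3 it is 2.15% to two decimals. Four million simulated trials at a true +4 points, with superiority stops counted as non-inferiority, gave 2.14%. Defining an inferiority stop against 0 or against +4 made no material difference.

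**5. The alternative reading.** Suppose every look could declare non-inferiority. The crossing probability of the four stated boundaries, with correlation √(tᵢ/tⱼ) between looks, is 2.38% one-sided. The stated 2.5% is therefore not exact on this reading either. The final level 0.043 and the coefficient 1.024 are the values for four equally spaced looks (calculated: constant 2.0243, two-sided 0.0429, inflation 1.0238). At 1/6, 1/3, 2/3 and 1 the corresponding values are 2.004, 0.0451 and 1.017.

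**6. Power.** With 5% loss, n per arm = 3626 × 0.95 / 2 = 1722.35 and SE = √(2 × 0.22 × 0.78 / 1722.35) = 0.01412, so 0.04/SE = 2.834.

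| Case, no true difference | Power |
|---|---|
| 95.7% interval, 5% loss: Φ(2.834 − 2.024) | 79.1% |
| 95% interval, 5% loss: Φ(2.834 − 1.960) | 80.9% |
| 95.7% interval, no loss (1813 per arm): Φ(2.907 − 2.024) | 81.2% |

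If every look could declare non-inferiority, the same boundaries with final drift 2.834 give about 79.6% at 5% loss.

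**7. Inflation.** A single test at one-sided 0.0215 needs ((2.0237 + 0.8416)/(1.960 + 0.8416))² = 1.046 times the fixed sample, or about 1762 per arm. That number is reached if loss is at most 1 − 2 × 1762/3626 = 2.8%.

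**8. Where the choice of interval decides the result.** At 5% loss, the largest observed difference that passes is 0.04 − 2.0237 × 0.01412 = +1.14 points with 95.7%, and 0.04 − 1.960 × 0.01412 = +1.23 points with 95%. With no true difference, the chance of landing between them is 80.9% − 79.1% = 1.8%.

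**The case against.** The strongest reply is that nothing is breached. A rate of 2.15% lies under the 2.5% ceiling, the 95.7% level is stated openly and identically in 5.1 and 5.4, and keeping the sequential interval at the end is an accepted conservative practice. One interval can then serve non-inferiority, superiority and inferiority conclusions alike. The 5% loss is a stated maximum, so the power shortfall is a worst case and under one point. All of this stands, and it limits the point to a correction of stated figures.

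It is also fair that the interim rules are only partly visible: the futility threshold is undefined, the plot is not shown, and the committee was guided by it rather than bound to it. If non-inferiority stops were intended, 5.4 omits them, and the error would be about 2.4%. That still does not give 2.5%.

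Three stronger readings should be resisted. A reader might infer that no interim rule could establish non-inferiority at all. That is not so, because a superiority stop would do it, although it spends almost no alpha. A reader might infer that 5.1 and 5.4 contradict each other on the final level. They do not: 2.5% is given as the overall error and 95.7% as the final interval. And a reader might infer that the 95.7% interval is wrong and must become 95%. The documents do not support that either, since the wider interval is valid, pre-specified and conservative.

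**Conclusion.** The point holds as a misstatement of operating figures. Under the stopping reasons that 5.4 lists, the primary non-inferiority claim has a one-sided type I error of about 2.15%, not 2.5%, and power of about 79.1% at the full 5% loss, not 80%. The effect is small and conservative, and the power shortfall disappears if loss is about 2.8% or less.

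This rests on four assumptions: the three listed stopping reasons are complete; information accrues in proportion to enrolment; the normal approximation holds at 22% mortality; and futility stopping, whose threshold is not given, is left out of the power figure. Futility stops could only lower the error and the power further.

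**What to change.** 1. In SAP 5.4, state for each interim interval which hypothesis it tests (difference against 0, against +4%, or both), and whether a non-inferiority stop was possible.
2. Keep the 95.7% interval in 5.1 as the criterion for non-inferiority.
3. In 5.4 and section 4, restate the type I error of the primary non-inferiority claim as about 2.15% one-sided, and the power as about 79% at 5% loss (81.2% with none). If non-inferiority stops were in fact available, state about 2.4% and 79.6% (at 5% loss) instead.

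The cost is a few sentences. The decision rule, the sample size and the data are unchanged, and the stated figures become slightly less favourable on power.

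An optional alternative is to judge non-inferiority on a two-sided 95% interval and keep the sequential interval for superiority or inferiority claims. Under the listed rules this is valid (2.5% error, 80.9% power at 5% loss). However, it relaxes the primary criterion in a SAP already marked final and after three interim looks, so it is defensible only if decided by people blinded to the accumulating data.
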